5 ANALYSIS REPORTS

This section describes the various analysis reports that will be created for this study.

5.1 SMC (interim) review

5.1.1 SMC report for annual reviews

As outlined in the A5315 monitoring plan, an analysis report will be prepared and distributed to the SMC members for each SMC review. The report will include analyses from the following subsections of **Section 7** broken down by treatment arm and dose cohort:

- Accrual
- Baseline characteristics
- Study status
- Treatment status
- HIV-1 RNA level at day 7
- Primary safety endpoint
- List of events

and a pooled (over treatment arm) summary of:

• Data and stored sample completeness

Note: Only a closed report will be generated.

5.1.2 SMC report for dose escalation

For the SMC review after completion of each cohort, to assess whether dose escalation can occur, an abbreviated analysis report will be prepared in order to expedite the dose escalation review. This report will include the following subsections of Section 7 broken down by treatment arm and dose cohort:

- Accrual
- Baseline characteristics
- Study status
- Treatment status
- HIV-1 RNA level at day 7
- List of events

Note: Only a closed report will be generated.

5.2 Final Analysis report

Unless otherwise noted, the final analysis report will include all subsections of **Section 7**.

6 GENERAL ANALYSIS CONSIDERATIONS

6.1 Lists of Data in Reports

Listings of data by individual study participants are described below to facilitate the interpretation of the study results. To help protect confidentiality of data, the content of these lists will be limited and will not include dates, participants' ACTG identifier numbers or other combinations of information that might identify an individual participant (except that these may be included in the confidential closed reports prepared for SMC review).

6.2 Study Treatment

The study treatment is Romidepsin (RMD) or Placebo for RMD (placebo).

6.3 Analysis Populations

Safety: All participants who have been exposed to study treatment/placebo will be included in the safety analyses.

Efficacy: For Cohorts 1-3, all participants who completed the study treatment infusion at Day 0 and with available outcome data will be included in the as-treated efficacy analyses.

For Cohort 4, all participants who completed all study treatment infusions and with available outcome data will be included in the as-treated efficacy analyses.

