Conditional evaluation weeks are only for participants whose next infusion will be delayed. The evaluations are performed weekly, unless otherwise specified, until the participant meets the criteria for the next infusion. If the participant does not meet the criterial for the next infusion by the last conditional evaluation week visit, then the participant will have the premature discontinuation evaluations performed per the SOE and then be taken off study.

Evaluations for hematology, potassium, magnesium, and/or plasma HIV-1 RNA expedited must be performed weekly as needed to meet the eligibility criteria for the next infusion. Otherwise, these evaluations should only be performed at the specific weeks indicated on the SOE.

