6.2.4 Event-Driven Evaluations

Cohorts 1 – 3

Participants with HIV-1 RNA levels \geq 200 copies/mL detected at the Day 7 visit (real-time HIV-1 RNA level) should be contacted immediately upon receipt of the Day 7 HIV-1 RNA results and asked to return as soon as possible (preferably within 72 hours) for a repeat HIV-1 RNA real-time PCR. If the repeat HIV-1 RNA

PCR level after Day 7 is \geq 200 copies/mL, the participant will complete both the Week 4/Day 28 and Week 8/Day 56 visits per section 6.1.1 or 6.1.2

Also, per section 7.1, participants who experience any >Grade 3 AE or clinical event, regardless of their Day 7 HIV-1 RNA level, will be seen at Week 8/Day 56.

Cohort 4

Participants with plasma HIV-1 RNA levels ≥50 copies/mL detected 7 days after any of the first three infusions should be contacted immediately upon receipt of the results by site staff and asked to return as soon as possible (preferably within 72 hours) for additional real-time testing. While this testing is being performed, the next infusion should be postponed. The participant should have weekly HIV-1 RNA levels tested, in addition to the other evaluations per the SOE, until the HIV-1 RNA level is <50 copies/mL, after which infusions and/or blood collections can continue per the Delayed Infusion SOE, section 6.1.4. Sites must promptly advise the A5315 core team upon initial receipt of any elevated HIV-1 RNA level ([contact]).

Also, per section 7.1, participants who experience any \geq Grade 3 AE or clinical event during an infusion will be followed as indicated in section 6.2.5.

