6.2.5 Discontinuation Evaluations

Evaluations for Randomized Participants Who Do Not Start Study Treatment No further evaluations are required for participants who do not initiate RMD/placebo infusion.

Cohorts 1 – 3

All CRFs must be completed and keyed for the period up to and including entry/Hour 0.

Cohort 4

All CRFs must be completed and keyed for the period up to and including Entry/Hour 0.

Premature Treatment and Study Discontinuation Evaluations Cohorts 1 – 3

Participants who receive RMD/placebo infusion but from whom blood is not collected at the 24-hour time point should remain on study for safety monitoring through Day 28.

Participants who prematurely discontinue study participation after receiving RMD/placebo or prior to the completion of RMD/placebo infusion, will have the premature study discontinuation evaluations performed per the SOE and recorded on CRFs.

Cohort 4

Participants who prematurely discontinue study treatment due to a ≥ Grade 3 AE or clinical event or for any other reason will not have any further infusions but will be followed on study/off study treatment. Participants will remain on their current step and complete the following visits: 24-hour post-infusion, 72-hour post-infusion, 7-day (1 week) post-infusion, and premature treatment/study discontinuation evaluations 4 weeks post-infusion and will then be taken off study.

Participants from whom the blood collection is not performed at more than one of the 24-hour time points after a RMD/placebo infusion will not have any further infusions but will be followed on study/off study treatment. Participants will remain on their current step and complete the following visits: 72-hour post-infusion, 7-day (1 week) post-infusion, and premature treatment/study discontinuation evaluations 4 weeks post-infusion and then will be taken off study.

Participants who prematurely discontinue study participation after receiving four RMD/placebo infusions or prior to the completion of four RMD/placebo infusions, will have the premature study discontinuation evaluations performed per the SOE and then will be taken off study. A replacement participant may be enrolled for each participant who prematurely discontinues the study, including participants who receive all four infusions but discontinue study participation prior to the week 11 visit.

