9.2 Outcome Measures

NOTE: Due to insufficient numbers of resting CD4+ T-cells available from some Cohort 4 participants to perform all the planned assays (e.g., cell-associated HIV-1 RNA, total HIV-1 DNA, histone acetylation, PTEF-b activation), those assays will be performed using peripheral blood mononuclear cells (PBMCs). The team carefully reassessed the priorities for the use of these cells based on advances in the field since the prior protocol version. Accordingly, the relevant objectives and outcomes measures sections have been updated.

- 9.2.1 Primary Endpoints
 - 9.2.1.1 Safety

Occurrence of Grade \geq 3 AE including signs/symptoms, lab toxicities, and /or clinical events that is probably, possibly or definitely related to study treatment (as judged by the core team, blinded to treatment arm) any time from the time of study treatment administration until 28 days after the administration.

- 9.2.1.2 Efficacy
 - 9.2.1.2.1 Change in plasma HIV-1 RNA levels from baseline (average of pre-entry and entry values) as detected by single copy assay at 24 and 48 hours (average) after the single administration of RMD or placebo in Cohorts 1 3.
 - 9.2.1.2.2 Change in plasma HIV-1 RNA levels from baseline (average of pre-entry and entry values) as detected by single copy assay before and 24 hours after each administration of RMD or placebo in Cohort 4.
 - 9.2.1.2.3 Change in cell-associated HIV-1 RNA levels in resting CD4+ T-cells from baseline to 24 hours after the single administration of RMD or placebo in Cohorts 1 – 3.
 - 9.2.1.2.4 Change in cell-associated HIV-1 RNA levels in **PBMCs** before and **24 hours** after each administration of RMD or placebo in Cohort 4.
- 9.2.2 Secondary Outcome Measures
 - 9.2.2.1 Changes in plasma HIV-1 RNA levels as detected by single copy assay from baseline to after the single administration of RMD or placebo in Cohorts 1 3 and after each administration of RMD or placebo in Cohort 4.

- 9.2.2.2 Change in cell-associated HIV-1 RNA levels in resting CD4+ T-cells from baseline to 14 days after the administration of RMD or placebo in Cohorts 1-3, and in PBMCs after each administration of RMD or placebo in Cohort 4.
- 9.2.2.3 Changes in histone acetylation in CD4+ **and CD8+** T-cells from baseline to after the single administration of RMD or placebo in Cohorts 1-3 and after each administration of RMD or placebo in Cohort 4.

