9.6 Analyses

For the primary safety analysis, Grade \geq 3 AEs attributed to the study treatment will be described separately for the treatment arm of each dose cohort, and for the combined placebo arms. All participants who have been exposed to the study treatment/placebo will be included in this analysis. As secondary analyses, all reported Grade \geq 2 AEs on all enrolled participants will be summarized for the treatment arm of each dose cohort, and combined placebo arms.

For the primary efficacy outcome measures of changes in plasma HIV-1 RNA level and cell-associated viral RNA levels in resting memory CD4+ T-cells **in Cohorts 1-3**, the analyses will be "as-treated" based only on participants who completed study treatment/placebo administration. Changes from baseline to scheduled study visits will be summarized with appropriate median plots, separately for the combined RMD and the combined placebo groups. A Wilcoxon rank sum test will be used for the comparison between the two combined groups for Cohorts 1 - 3. Analysis for the primary efficacy outcome measures in Cohort 4 will use the same approach between RMD and placebo.

Secondary outcome measures will be explored in a similar fashion. Additionally, a generalized Wilcoxon test will be used to compare the changes in plasma HIV-1 RNA by SCA in Cohort 4 between RMD and placebo to account for potential censoring due to undetectable SCA value at baseline. If proportions of undetectable SCA values are high, changes in SCA levels may also be analyzed as categorical data (increase from baseline vs. decrease from baseline vs. undetermined). Furthermore, longitudinal SCA levels per participant will be plotted.

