7.13 Cohort 4 primary efficacy outcomes

7.13.1 Change in plasma HIV-1 RNA levels from baseline (average of pre-entry and entry values) as detected by single copy assay before and 24 hours after each administration of RMD or placebo in Cohort 4.

The analysis of 7.13.1 will be combined with 7.14.1. The available timepoints are: pre-entry (-35 to -28 days), pre- & 24hr post-infusion for all 4 infusions, and 72hr post-2nd-infusion

SCA values below the limit of detection (LOD) will be imputed as equal to half the limit of detection (i.e., if LOD=0.4 copies/mL, results < 0.4 copies/mL will be imputed as 0.2 copies/mL).

a. Tables:

- Completeness of data for all measurement time points
- N (%) of SCA value < LOD at all measurement time points
- Baseline SCA: N, median, 25th and 75th percentiles, min, max
- Pre- and 24hr post-infusion SCA for each infusion and 72hr post-2nd-infusion: N, median, 25th and 75th percentiles, min, max
- Change (at each post-entry time point baseline) SCA: N, median, 25th and 75th percentiles, min, max
- Change (post-infusion time point pre-infusion time point for each infusion) SCA: N, median, 25th and 75th percentiles, min, max

NOTE: Baseline averages will be calculated using log10-transformed SCA values.

Wilcoxon rank sum test will be used for the comparison between groups. Wilcoxon signed rank test will be used to test within-group changes for RMD group. Two-sided 95% confidence intervals for the shift will be calculated based on Hodges-Lehmann estimator.

b. Figure:

- Longitudinal median (Q1, Q3) plots for all measurement time points by RMD and placebo.
- Longitudinal, participant-specific, (spaghetti) plots for all measurement time points with open symbol for values below the LOD and different symbols/colors for RMD and placebo.

7.13.2 Change in cell-associated HIV-1 RNA levels in PBMCs before and 24 hours after each administration of RMD or placebo in Cohort 4.

The analysis of 7.13.2 will be combined with 7.14.2. The available timepoints are the same as 7.13.1 and 7.14.1. The same analysis approach will be used as in 7.13.1 (except N (%) below LOD).

NOTE: Cell-associated RNA results below the detection limit are imputed with 1 copy/million PBMCs.

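### Cohort 4 efficacy is analysed only in participants who completed all four infusions, so valid infusion-1 data from anyone who stops later are left out of the infusion-1 comparison

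*SAP*

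**What the plan says.** - **Analysis set.** SAP 6.3 states: "For Cohort 4, all participants who completed all study treatment infusions and with available outcome data will be included in the as-treated efficacy analyses". SAP 7.13 to 7.15 name no other Cohort 4 efficacy set. The safety set keeps everyone exposed.
- **Endpoint.** Protocol 9.2.1.2.2 measures plasma HIV-1 RNA "as detected by single copy assay before and 24 hours after each administration of RMD or placebo in Cohort 4", and 9.2.1.2.4 does the same for cell-associated RNA in PBMCs. SAP 7.13.1 tabulates "Change (post-infusion time point pre-infusion time point for each infusion) SCA" (post minus pre) as well as change from baseline. It compares groups by the Wilcoxon rank sum test and tests within-romidepsin change by the signed rank test.
- **Protocol analysis rule.** For Cohorts 1-3, protocol 9.6 uses those who completed treatment administration. It then adds: "Analysis for the primary efficacy outcome measures in Cohort 4 will use the same approach between RMD and placebo". It does not say whether completion is judged per infusion or over all four.
- **Ways to leave after infusion 1.** Under protocol 6.2.5, participants who stop treatment for a Grade 3 or higher event or any other reason, or who miss more than one 24-hour collection, "will not have any further infusions but will be followed on study/off study treatment". Under 6.2.3, a participant leaves the study if "the participant does not meet the criterial for the next infusion by the last conditional evaluation week visit". The criteria for each next step (4.5, 4.7, 4.9) include RNA below 50 copies/mL and limits on neutrophils, hemoglobin and platelets.
- **Replacement.** Protocol 9.4 and 9.4.3 say that non-completers will be replaced. Protocol 6.2.5 is weaker: "A replacement participant may be enrolled for each participant who prematurely discontinues the study".

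**The concern.** The infusion-1 comparison needs only infusion 1, and its samples exist: SCA and PBMC collections are scheduled before and 24 hours after that infusion, and those who stop still complete the post-infusion visits of their current step. Requiring three further infusions conditions the comparison on events after randomisation.

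Treatment may affect some of those events. Raising HIV expression is the intended effect of romidepsin, and plasma RNA is one of the criteria for continuing. Protocol 2.2 lists bone marrow suppression among common first-cycle toxicities, and blood counts are another criterion. Toxicity can also end treatment directly. If remaining to infusion 4 is related to the 24-hour response, the infusion-1 comparison is biased, in a direction that cannot be known in advance. A replacement fills the place of the person who left but does not undo the selection.

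The placebo arm has three participants, so discarding even one usable placebo value matters.

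**Working it through.** **Inputs.** Protocol 9.4.2 gives 12 romidepsin and 3 placebo participants, an SD of 0.33 for the log10 change in cell-associated RNA, and a difference of 0.79 log10 at 80% power with a two-sided 5% Wilcoxon test. It gives an SD of 0.32 for the SCA change in Cohorts 1-3. No loss rate is given.

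**The plan's own figure.** At 0.79 with 12 vs 3 and SD 0.33, simulated exact rank-sum power is 0.89 (200,000 trials, normal responses), and 80% power is reached at 0.70. The stated 80% at 0.79 is not reproduced; it is conservative, and nothing below depends on it. The baseline used here is 0.89.

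**Shift in the mean.** Suppose m romidepsin participants leave after infusion 1 and are replaced, so that the 12 analysed are what remains of 12 + m. Let r be the correlation between the variable that drives stopping and the 24-hour response. If higher responders leave, the shift is

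−r × SD × S / 12,

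where S is the expected sum of the m largest of 12 + m standard normal values: 1.668, 2.911 and 3.932 for m = 1, 2, 3. At r = 1 and SD 0.33:

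- m = 1: 0.33 × 1.668 / 12 = 0.046
- m = 2: 0.33 × 2.911 / 12 = 0.080
- m = 3: 0.33 × 3.932 / 12 = 0.108

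Simulation agrees. All cells at SD 0.33:

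| r | m = 1 | m = 2 | m = 3 | Power at 0.79 (m = 1, 2, 3) |
|---|---|---|---|---|
| 0 | 0 | 0 | 0 | 0.89, 0.89, 0.89 |
| 0.3 | 0.014 | 0.024 | 0.032 | 0.88, 0.87, 0.87 |
| 0.5 | 0.023 | 0.041 | 0.054 | 0.88, 0.87, 0.86 |
| 1 | 0.046 | 0.080 | 0.108 | 0.87, 0.86, 0.85 |

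The shifts are downward when higher responders leave and upward when lower responders leave; the power column is for the downward case. SD 0.32 gives almost the same values (0.022 to 0.053 at r = 0.5). Relative to 0.79: 0.023/0.79 = 2.9%, 0.054/0.79 = 6.8%, 0.108/0.79 = 13.7%.

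**What recovered data add.** Exact power by group size, SD 0.33:

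| RMD vs placebo | at 0.79 | at 0.60 |
|---|---|---|
| 12 vs 3 | 0.89 | 0.68 |
| 13 vs 3 | 0.88 | 0.66 |
| 14 vs 3 | 0.90 | 0.70 |
| 15 vs 3 | 0.89 | 0.68 |
| 12 vs 4 | 0.94 | 0.77 |
| 12 vs 2 | 0.74 | 0.51 |

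Extra romidepsin values add no useful power. The dip at 13 vs 3 comes from the attained level of the exact test: 22/560 = 0.039, against 22/455 = 0.048 for 12 vs 3. Placebo values do matter. If one placebo participant leaves and is replaced, keeping the infusion-1 value gives 12 vs 4. If that participant is not replaced, the completer rule leaves 12 vs 2 where 12 vs 3 was available. At 12 vs 1 the smallest two-sided p is 2/13 = 0.154, so significance is impossible.

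**How likely is any exit?** As an assumption only: at 5%, 10% or 20% per participant, the chance that at least one of 15 stops is 1 − 0.95^15 = 54%, 1 − 0.90^15 = 79% and 1 − 0.80^15 = 96%.

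**The case against.** The completer set looks deliberate. Cohort 4 treatment is four doses, the sample size counts evaluable participants, non-completers are replaced (protocol 9.4), and not receiving all four infusions is a study-discontinuation criterion (8.2). A constant group across infusions is a legitimate aim. These are replacement and discontinuation rules, however. None requires the infusion-1 comparison to leave out later stoppers, and for a single infusion the approach of 9.6 points equally well to completion of the infusion being analysed.

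The likely effect is small, and this stands. The standard error of a 12 vs 3 mean difference is 0.33 × √(1/12 + 1/3) = 0.21, so the shift is about 0.1 to 0.25 standard errors at correlation 0.5 and about 0.5 at correlation 1.

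Exits may be rare, and this also stands. A raised RNA only postpones the next infusion, "after which infusions and/or blood collections can continue per the Delayed Infusion SOE", and there are eight weekly conditional visits before a participant is taken off. The half-life is about 3 hours. The marrow findings come from cancer dosing, whereas the two HIV studies summarised in protocol 2.2 at 5 mg/m² saw no Grade 3 or 4 study-related events in one and no Grade 4 events in the other. Protocol 9.4.1 assumes negligible Grade 3 or higher events on placebo, so a placebo exit would more likely follow missed collections, illness or withdrawal. The 12 vs 2 case also needs a placebo participant who is not replaced.

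The SDs are borrowed. The 0.33 is stated for cell-associated RNA per million CD4 cells, not PBMCs. The 0.32 is for averaged 24/48-hour SCA in participants screened at 0.4 copies/mL or above, which Cohort 4 does not require. Normal responses also ignore values below the detection limit.

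Finally, the remedy is partial. Infusions 2 to 4 remain conditional on continuing, a participant stopped during infusion 1 is excluded either way, and someone who missed the infusion-1 24-hour sample has no value to recover.

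**Conclusion.** The concern holds. SAP 6.3 excludes usable infusion-1 data from anyone who stops later, and nothing in SAP 7.13 to 7.15 overrides it. The result is avoidable selection on post-randomisation events in a primary comparison, and possible loss of scarce placebo data.

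Severity is minor to moderate. With one to three replaced romidepsin exits, the bias is 3-7% of the 0.79 design difference at correlation 0.5 and at most 14% at correlation 1; it is zero if stopping is unrelated to response. Power falls by no more than about 0.04. The case for change on the romidepsin side is less selection, not more power; on the placebo side power is also at stake. All sizes rest on an assumed number of exits, normal responses and the borrowed SDs. If nobody stops early, the change alters no result. It should be made because it is cheap and can be settled before unblinding.

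**What to change.** Replace the Cohort 4 sentence in SAP 6.3, with conforming wording in protocol 9.6, along these lines:

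> For Cohort 4, the efficacy set for infusion k is every participant who completed infusions 1 to k and has the data that the analysis needs (baseline and post-infusion-k values for change from baseline; pre- and post-infusion-k values for within-infusion change), whether or not later infusions were given.

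Keep four-infusion completers as a sensitivity analysis; this also gives a constant group across infusions. State that only the infusion-1 comparison is freed from this selection. SAP 7.2, 7.3, 7.6 and 7.7 already report exclusions, replacements, reasons for non-completion and day-7 RNA, so SAP 7.6 needs only one added line: infusion delays by arm and reason.

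Two sets of passages should be reconciled at the same time. Replacement is mandatory in protocol 9.4 and 9.4.3 but optional in 6.2.5, and same-arm replacement is stated only for infusions stopped for reasons other than treatment-attributed Grade 3 or higher events. Protocol 7.1.2-7.1.3 and 8.1 also differ on stopping after a Grade 3 or higher event that follows an infusion; no clinical rule is proposed here.

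The cost is one sentence in each document, one table line, and assay of stored samples from non-completers. Different participants will contribute at different infusions, which the completer sensitivity analysis covers.

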6.4 Definition of "Day 0" and "baseline"

"Day 0" is defined as the day of study registration (variable **ONSTDT** from **ADM0020**). In the study protocol, this is often referred to as entry date. "Baseline" is defined as the last evaluation on or before Day 0.

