6.2.2 Entry Evaluations

Cohorts 1 – 3

Entry/Hour 0 evaluations must occur within 24 hours after randomization and at least 7 days after the second pre-entry visit (-21 to -7 days) evaluations, unless otherwise specified.

All entry/Hour 0 specimens must be obtained and pregnancy test reported before initiating RMD or placebo infusion.

Cohort 4

Entry evaluations must occur within 24 hours after randomization.

All entry/Hour 0 specimens must be obtained and pregnancy test reported before initiating the first RMD or placebo infusion.

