6.2.3 Post-Entry Evaluations

The RMD/placebo infusion should be completed in 4 hours. In the event that the infusion requires more than 4 hours, the time of infusion completion is still to be considered Hour 4.

Post-Treatment Evaluations, Cohorts 1 – 3

Hour 4 evaluations begin immediately following completion of RMD/placebo infusion. All subsequent evaluation time points are to be calculated from the infusion completion time which is considered Hour 4 regardless of whether the actual time from infusion start to completion took less or more time than 4 hours (ie, Hour 6 is 2 hours after the infusion has finished, Hour 8 is 4 hours after the infusion has finished, etc.).

Post-Treatment Visit Schedule, Cohorts 1 – 3

Study visits and collection time points must be scheduled as indicated in the Schedule of Events (SOE) \pm 15 minutes for Hour 2, 4 (except for ECG which has a window of +0-60 minutes), 6, 8, 12; \pm 2 hours for Hour 24; \pm 4 hours for Hour

48/Day 2; \pm 2 days for Day 7 and Week 2/Day 14, and -1 day to +2 days for Week 4/Day 28. Per sections 6.2.4 and 7.1, participants may be required to return for a Week 8/Day 56 visit \pm 4 days.

Study Completion Evaluations, Cohorts 1 – 3

Week 4/Day 28 evaluations will serve as the study completion evaluations for participants who have maintained an HIV-1 RNA level of < 200 copies/mL by standard ultrasensitive assay since the Day 7 visit. See section 6.2.4 for participants who have an HIV-1 RNA level of \geq 200 copies/mL at the Day 7 visit.

Also, these evaluations will be the study completion evaluations for participants who did not experience any \geq Grade 3 AE or clinical event (per section 7.1).

Post-Entry Visit Schedule, Cohort 4

Study visits and collection time points must be scheduled as indicated in the Cohort 4 SOE, section 6.1.3. The windows are ±6 hours for day 1 (24 hours post-infusion), ±1 day for day 3 (72 hours post-infusion), and ±1 day for day 7 (7 days post infusion). For participants whose second, third, and/or fourth infusion must be delayed for any reason, the Delayed Infusion SOE, section 6.1.4, must be followed until the end of the study follow-up for that participant. Participants' visits will be scheduled per this SOE beginning with the first delayed infusion.

Sites should notify the A5315 core team if any infusion will be delayed ([contact]).

Conditional Evaluation Weeks, Cohort 4

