Cell-associated HIV-1 RNA will be measured in resting CD4+ cells from blood collected on Day 0 prior to RMD/placebo infusion and then about 24 hours after the start of the infusion and about 14 days following infusion.

Cell-associated HIV-1 DNA will be measured in resting CD4+ cells from blood collected within 7 days prior to RMD/placebo infusion and then about 24 hours after the start of the infusion and about 14 days following infusion; see section 6.2.3 for timing.

Cohort 4

Cell-associated total HIV-1 RNA will be measured in **PBMCs** cells from blood collected at pre-entry visits, on Day 0 prior to RMD/placebo infusion, and then about 24 and 72 hours after the start of each infusion.

Cell-associated HIV-1 DNA will be measured in **PBMCs** from blood collected prior to RMD/placebo infusion and then about 24 and 72 hours after the start of each infusion.

Stored PBMC for Virology Studies

Stored PBMCs will be used for:

- Future virology studies
- Total CD4+ T-cells for Histone Acetylation and PTEF-b Phosphorylation Assays: Positive transcription elongation factor-b (PTEF-b) phosphorylation will be assessed in total CD4+ cells isolated from cryopreserved stored PBMC per the SOE.

Stored PBMC for **qVOA** (Cohort 4 only)

At the time points indicated in section 6.1.3 SOE, a separate blood collection will be made and PBMCs will be stored for a **quantitative viral outgrowth** assay.

Resting CD4+ T-cells for Ex vivo PMA/Ionomycin and RMD Inducible HIV-1 RNA Expression

Cohorts 1 – 3

Resting CD4+ T cells will be isolated from blood collected per the SOE. Cells will be cultured in the presence of RMD or PMA/Ionomycin. At various times poststimulation, HIV-1 RNA levels will be measured in culture supernatants by Abbott real-time assay.

- 6.3.11 Pharmacokinetic (PK) Studies (Refer to Section 10.0)
 - NOTE: For PK collections, blood must be drawn from the opposite side of the body from that used for the RMD infusion.

Refer to the LPC for collection, processing, storage, and shipping details.

Cohorts 1 – 3

Blood will be drawn following completion of the RMD infusion for determination of RMD and ARV (RAL, EFV, or DTG) plasma levels per the SOE and section 10.2. The date and time of the last three doses of ARV taken immediately prior to the pre-infusion blood sample must be recorded.

Cohort 4

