6.3.12 RMD or Placebo for RMD Infusion

For correct RMD dosing calculate BSA per section 5.1. See section 6.3.4, Clinical Assessments, Study Treatment Modifications.

Cohorts 1 – 3

RMD will be administered as a single 4-hour intravenous infusion starting at entry/Hour 0. Potassium and magnesium levels will be assessed prior to infusion at the pre-entry visit (day -21 to -7). Blood potassium and magnesium values must be within normal limits. If the pre-entry potassium and/or magnesium value(s) is below the site's clinical laboratory's limit of normal, the participant should be supplemented as medically indicated, retested, and evaluated prior to study entry. If the pre-entry potassium and/or magnesium value(s) is high, the value(s) should be retested, and evaluated prior to study entry. The repeated pre-entry potassium and/or magnesium values must be within normal range for the site's limit of normal for study entry. Given blood volume constraints in this study, sites should use pediatric volume tubes whenever feasible.

Cohort 4

RMD will be administered as a 4-hour intravenous infusion at four time points, as indicated in the Cohort 4 SOE, section 6.1.3 or, as warranted, in the Cohort 4 - Delayed Infusion SOE, section 6.1.4, . See section 6.3.7 for pre-infusion safety testing.

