6.6 Visit schedule and definition of "Day" and "Week" for analysis purposes

Days and Weeks on study will be based on the study treatment administration dates (i.e., will be " anchored" on the infusion timing) and will use the protocol-specified windows. The protocol schedule of events for Cohort 4 is provided in **Appendix 1**.

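### SAP 6.4 sets baseline by registration date with no pre-infusion condition; applied literally by date in Cohorts 1-3 it can select a post-dose sample or exclude Hour 0

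*SAP*

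**What the plan says.** SAP 6.4 takes Day 0 from a date field, the day of study registration, and notes that the protocol often calls this the entry date. Baseline "is defined as the last evaluation on or before Day 0". No clock time and no condition about the infusion is given. This is the only general baseline rule in the SAP.

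Neighbouring sections use another anchor. For Cohorts 1-3, SAP 6.3 takes into the efficacy set "all participants who completed the study treatment infusion at Day 0", provided that outcome data are available. SAP 6.6 says: "Days and Weeks on study will be based on the study treatment administration dates".

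Some outcomes carry their own wording. SAP 7.10.1 (primary plasma HIV-1 RNA by single-copy assay, SCA) averages pre-entry and entry values on the log10 scale, and 7.11.1 is folded into it. SAP 7.10.2 (primary resting-cell RNA) states no baseline rule. SAP 7.11.4 (histone acetylation) tabulates change from baseline but tests change from pre-dose. SAP 7.12.6 equates baseline with pre-dose in its fold change. SAP 7.11.3, 7.11.5 and 7.12.7 say only baseline.

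In the protocol, section 6.2.2 states for Cohorts 1-3: "Entry/Hour 0 evaluations must occur within 24 hours after randomization". It also requires Hour 0 specimens to be taken before the infusion, a condition that SAP 6.4 does not carry over. Section 6.3.12 says: "RMD will be administered as a single 4-hour intravenous infusion starting at entry/Hour 0".

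**The concern.** A change from baseline means little if the baseline can be a treated value. Cohorts 1-3 have research draws at Hours 6 and 12, which can share a calendar date with registration. A program that compares sample dates with the registration date, as 6.4 literally asks, would then choose the latest of them.

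The reverse problem arises when infusion falls on the date after registration. The true pre-dose sample is then dated after Day 0, and the rule discards it.

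At stake are the early changes in several secondary and exploratory outcomes and, in a narrower case, the availability of a baseline for one primary outcome. The plan also uses Day 0 in two senses within three short sections.

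**Working it through.** The plan gives no figure to reproduce. The check is of dates against the schedule for Cohorts 1-3 (protocol Tables 6.1.1-1 and 6.1.2-1).

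**Inputs**

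| Material | Pre-dose draws | First post-dose draws |
|---|---|---|
| Stored virology PBMC | Screening, Day -35 to -30, Hour 0 | Hours 6, 12, 24 |
| Histone acetylation | Hour 0 only | Hours 12, 24 |
| Stored immunology plasma/PBMC | Hour 0 only | Hour 48 |
| D-dimer | Hour 0 only | Day 7 |
| Resting CD4+ cells for RNA/DNA | Day -7 to Hour 0 | Hour 24 |

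Protocol 6.3.10 says that P-TEFb phosphorylation (7.12.7) "will be assessed in total CD4+ cells isolated from cryopreserved stored PBMC per the SOE". I take the total-cell outcomes 7.11.3 and 7.11.5 to come from the same stored virology PBMC, because their listed times match its draws.

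**Case 1: infusion on the registration date**

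Let the infusion start at clock time s, in hours. With a nominal 4-hour infusion, Hour h falls at s + h, within 15 minutes. It carries the registration date if s + h < 24.

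- Hour 12: s < 12. A start before 12:00 makes Hour 12 the last evaluation on Day 0. Example: start 08:00, Hour 12 at 20:00.
- Hour 6: s < 18. A start from 12:00 to before 18:00 makes Hour 6 the last. This reaches only 7.11.3 and total-cell 7.11.5, because 7.11.4 and 7.12.7 list no 6-hour value.
- A start at 18:00 or later leaves Hour 0 as baseline.

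Listed changes exposed to an Hour 12 baseline:

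- 7.11.3: 7 (6, 12, 24, 48 hours; 7, 14, 28 days)
- 7.11.5, total-cell part: 7 (same times)
- 7.12.7: 5 (12, 24, 48 hours; 7, 14 days)
- Total: 7 + 7 + 5 = 19
- Also the 5 changes in the 7.11.4 tables, but not its test, which is worded from pre-dose.

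Effect on a change at time t:

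Y(t) - Y(12) = [Y(t) - Y(0)] - [Y(12) - Y(0)]

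The 12-hour change is 0 by construction. Every later change is shifted by that participant's own 12-hour response. The documents do not give the size of that response.

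**Case 2: infusion on the next calendar date**

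Hour 0 is dated Day 0 + 1 and fails the rule. Outcomes with no earlier draw have no baseline: 7.12.2 (3 changes), 7.12.3 (3) and 7.12.4 (2), so 3 + 3 + 2 = 8, plus the 5 changes in the 7.11.4 tables and the baseline percentage in 7.12.5. Outcomes from stored virology PBMC fall back to the Day -35 to -30 draw. I leave out 7.12.1, since CD4+/CD8+ percentages are also taken at screening.

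For primary outcome 7.10.2 the protocol gives two accounts. Section 6.3.10 states: "Cell-associated HIV-1 RNA will be measured in resting CD4+ cells from blood collected on Day 0 prior to RMD/placebo infusion". The schedule allows Day -7 to Hour 0. Only a draw on the infusion day would be lost.

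To show scale only, suppose one participant is lost from 7.10.2, with the SD of 0.33 and the planned 36 versus 9 of protocol 9.4.2, and SE = 0.33 × sqrt(1/n_RMD + 1/n_placebo):

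- 36/9: 0.1230
- 36/8: 0.1290 (+4.9%)
- 35/9: 0.1233 (+0.3%)
- One random loss at 4:1: 0.2 × 4.88% + 0.8 × 0.285% = 1.2% on average

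In Cohort 4 the first virology or immunology draw after an infusion is at 24 hours, so Case 1 is essentially a Cohorts 1-3 matter. The 24-hour allowance after randomization applies there too.

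**The case against.** The strongest reply is that nobody would do this. SAP 6.6 ties analysis days to the infusion and to protocol windows. The protocol treats later hours as post-entry: section 6.2.3, on post-entry evaluations, says "Hour 4 evaluations begin immediately following completion of RMD/placebo infusion". A sample labelled post-entry Hour 12 is not an evaluation on or before entry, and a 12-hour change of exactly zero for everyone would be noticed. SAP 7.11.4 and 7.12.6 already use pre-dose. SAP 7.11 and 7.12 default to the primary approach, and the stored virology PBMC has the pre-entry and entry draws needed to form the SCA-type average.

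Most of this stands as a limit on harm. A visit-based reading does avoid Case 1, and the pre-dose intent is visible. It does not remove the conflict. SAP 6.4 states a rule on a date field, and that rule followed literally gives the wrong sample for an ordinary morning infusion. The default to the primary approach is not decisive, because 7.10.1 averages two visits and 7.10.2 is silent. The independent coding in SAP 6.7 covers the primary analyses only.

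On Case 2, the reply is that randomization and infusion are both placed at entry, so next-day infusion may be rare. That also stands: the protocol permits it, but nothing shows that it occurred. Read literally, SAP 6.3 would in any case drop such a participant from the efficacy set, although SAP 7.10 restates that population without reference to Day 0.

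**Conclusion.** The inconsistency is real and minor. SAP 6.4 anchors on registration and omits a pre-infusion condition, while 6.3, 6.6 and the pre-dose wording in 7.11.4 and 7.12.6 point to the infusion. The same-day consequence rests on a calendar-date derivation, a nominal 4-hour infusion and the assumed start times. The next-day consequence rests on an event of unknown frequency.

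A reader might infer more than the documents support:

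- *That the primary results are compromised.* SCA (7.10.1) has its own baseline and is unaffected. Resting-cell RNA (7.10.2) has no Hour 6 or Hour 12 draw. It is exposed only with next-day infusion and a pre-dose draw on the infusion day, and the SE figures above assume a single hypothetical loss.
- *That a bias in log10 units can be stated.* It cannot. The 12-hour response is not given, and a log10 scale would not suit 7.11.4, which uses absolute change in fluorescence intensity.
- *That the histone acetylation test is affected.* Its wording is already from pre-dose; only the tables say baseline.

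**What to change.** In SAP 6.4:

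- Define baseline as the last evaluation collected before the start of the first infusion, by collection date and time, unless an endpoint states otherwise. Keep the log10 average of pre-entry and entry values for 7.10.1 and 7.13.
- Define Day 0 as the date of the first infusion, so that 6.3, 6.4 and 6.6 agree. Use the registration date as the fallback for randomized participants who are never infused, a group that protocol 6.2.5 provides for.

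In SAP section 7:

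- Use pre-dose throughout 7.11.4.
- State whether 7.11.3, total-cell 7.11.5 and 7.12.7 use Hour 0 or the pre-entry/entry average.

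The cost is a few sentences in the SAP and a date-time check in the derivation program. No new data are needed.
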